#### 11.2 End-of-Study Visits For Subjects who Terminate Prematurely

Subjects who terminate prematurely, for any reason, should have a final safety visit completed at approximately 30 days after the last dose received, or if that timepoint is already passed, as soon as possible. This final visit should include the procedures scheduled for Day +28 after Dose #3. If they cannot complete a visit, safety follow-up should be conducted by phone.

[name] 5/31/15 10:25 AM Deleted: Table 2-4

# **12. SAFETY EVALUATIONS**

Clinical trials sponsored by Dartmouth College will be conducted in accordance with Good Clinical Practices for collecting and reporting safety information. Safety and tolerability will be evaluated based on AEs, vital signs, physical exams, laboratory tests and other assessments.

### 12.1 Definitions

### 12.1.1 Adverse Event (AE)

An Adverse Event is any untoward medical occurrence temporally associated with the use of a medical product in a subject, *whether or not* the event is considered causally related to the medical product. An AE can be a new occurrence or an existing process that increases significantly in intensity or frequency.

An AE in a clinical trial may be *any* of the following:

- Unfavorable and unintended *symptom reported by the subject* subjects will be encouraged to report treatment-emergent AEs spontaneously; general, non-directed questioning may also be used to elicit reports of AEs;
- Clinical *sign detected by the Investigator* observations by other study personnel will be reported to the Investigator for evaluation;
- Is a treatment-emergent new or increased abnormal result from a *laboratory study* or other *diagnostic procedure*.

### 12.1.2 Pregnancy

Pregnancy is not an AE. Pregnancy testing will be performed as scheduled. If a female subject becomes pregnant during a study, the Medical Monitor must be notified in writing within five days. Follow-up information regarding the outcome of the pregnancy and any postnatal sequelae in the infant will be obtained.

### 12.1.3 Serious Adverse Event (SAE)

- An AE is serious when the subject outcome is one or more of the following:
  - Death.
  - Life-threatening, meaning that the subject was at immediate risk of death from the event at the time that the event occurred. It does not include an event which hypothetically might have caused death if it occurred in a more severe form.
  - Hospitalization, initial or prolonged, meaning that a hospital admission and/or prolongation of a
    hospital stay was required for the treatment of the AE, or occurred as a consequence of the event.
    It does not include a pre-planned elective hospital admission for treatment or diagnostic
    procedures, or, in general, a hospital admission of less than 24 hours duration.
  - Disability or incapacity that is persistent or significant.
  - Congenital anomaly or birth defect.
  - Important medical event that, although not immediately life-threatening, requires intervention in order to prevent one of the other serious outcomes listed above. Examples of such events are allergic bronchospasm requiring intensive treatment in an emergency room or at home; blood dyscrasias or convulsions that do not result in hospitalization; or the development of drug dependency or drug abuse.

<sup>22 A medical product may be a drug or a device being used either prior to or after regulatory approval. The medical product in this protocol will hereafter be referred to as study drug (synonym: investigational agent).

### 12.1.4 Suspected, Unexpected Serious Adverse Reaction (SUSAR)

A SUSAR is defined as an SAE that meets both the following criteria with respect to study drug:

- Suspected is assessed as related or possibly related to study drug (see Section 12.3.3);
  - *Unexpected* compared to the study drug-related AEs described in Investigator's Brochure, the event meets *any* of the following criteria:
    - The event was not previously described;
    - The event is now characterized as more severe (see Section 12.3.4);
    - The event is now characterized more specifically (e.g., an event of "interstitial nephritis" in a subject receiving an agent previously described as associated with "acute renal failure").

In clinical trials involving ill patients, events considered related to the natural history of the disease under study or to lack of efficacy (that is, the event is considered more likely related to those factors than to other factors, including study drug) are not considered "unexpected". Lack of efficacy is recorded as specified elsewhere in the Protocol.

#### 12.1.5 Investigator Assessment of Safety Laboratory Tests

The Investigator will review the results of all Safety Laboratory tests (see Section 10.3.1 and Section 10.3.2) and designate any results outside of the reference range as *either* of the following:

- Abnormal, not clinically significant (NCS)
- Abnormal, clinically significant (CS).

In making this judgment, the Investigator will consider all available information, including the patient's clinical condition, all available laboratory results (central and local), and the potential for false positive test results. In addition, laboratory studies that result in the actions specified in Section 12.1.1 will be classified as "abnormal, clinically significant".

Any result assessed as "abnormal, clinically significant" will be recorded as an AE *unless* it is consistent with one or more of the following:

- Process noted in the medical history.
- Ongoing adverse event already recorded;
- Expected course of the primary disease under study (if applicable);

### 12.2 Collecting and Recording Adverse Events

Procedures for the collection and recording of AEs are as follows:

- From obtaining informed consent through administration of the first dose of study drug (Day 1), there will be active surveillance to identify all AEs; events will be recorded in the medical history.
- Both at study visits and scheduled phone calls subjects will questioned using both a scripted checklist to elicit anticipated vaccine-related adverse events, as well as open-ended queries to elicit unanticipated events.
- From administration of the first and second doses of vaccine through the phone calls scheduled for day 28 post-dosing, and from the third dose of vaccine through the visit scheduled for day 28 post-dosing, there will be active surveillance to identify all AEs; events will be recorded in the ISR or AE portions of the CRF, as appropriate.
- At the visit for administration of Doses 2 and 3 and at the End-of-Study visit (Day 173-187), subjects will be asked about AEs with onset >28 days after the most recent dose and all events qualifying as SAEs will be recorded.
- After the EOS, surveillance will be passive (only events brought to the investigator's attention will be considered) and only events assessed as SUSARs will be recorded (see Section 12.4).

### 12.3 Characterizing Adverse Events

For each AE recorded the following characteristics will be noted.

### 12.3.1 Description of Event

The diagnosis or description will be as specific and complete as possible (i.e., "lower extremity edema", rather than just "edema"). Whenever possible, signs and symptoms due to a common etiology will be reported as an integrated diagnosis; for example, cough, runny nose, sneezing, sore throat and head congestion would be reported as "upper respiratory infection".

#### 12.3.2 Date and Time of Onset

The date and time at which the event was first apparent. Table 12-1, summarizes the basis for reporting the date and time of onset for the different types of AEs described in Section 12.1.1.

#### Table 12-1. Reporting the Date and Time of Onset of AE for Different Types of Events

Type of Event	Examples	Source of Date and Time of Onset
Symptom	Headache, feverish, paresthesias	When first experienced by the patient
Sign (Finding)	Elevated BP, enlarged liver on physical exam	When first observed by the Investigator or other study staff
Laboratory / diagnostic result	Neutropenia, hyperglycemia, lesions on brain scan	When lab sample was obtained or diagnostic study performed

The time of onset of symptoms may be appreciably earlier than the date and time the Investigator becomes aware of the event. Some events may be apparent to the patient and Investigator independently, and information from each may contribute to the final report. For example, a patient may report the onset of a rash two days before being seen by a physician who makes a diagnosis of herpes zoster based on appearance and laboratory confirmation. In that case, there is a single AE, with the date of onset based on the date of the initial observation by the patient and a specific description (herpes zoster) based on the clinical exam and tests.

#### 12.3.3 Relationship to Study Drug

This determination is based on the Investigator's clinical judgment and the Medical Monitor's clinical judgement regarding the likelihood that the study drug caused the AE and may include consideration of some or all of the following factors:

- Alternative possible causes of the AE, including the subject's underlying disease or co-morbid conditions, other drugs, other host and environmental factors;
- Temporal sequence between the exposure to study drug and the AE;
- Whether the clinical or laboratory manifestations of the AE are consistent with known actions or toxicity of the study drug;
- Whether the AE resolved or improved with decreasing the dose or stopping the study drug (i.e., dechallenge); or recurred or worsened with re-exposure to the drug (i.e., rechallenge).

The relationship between the study drug and the AE will be described using one of the following categories:

- *Related* the study drug is more likely the cause of the AE than other factors;
- **Possibly related** there is a *reasonable* possibility that the study drug is the cause of the AE, including that the study drug and another factor(s) are equally likely as causes of the AE;
- *Unlikely related* another factor is considered more likely the cause of the AE than the study drug;
- *Not related* another factor is considered to be the cause of the AE.

**Confidential and Proprietary** 

[name] 5/31/15 10:25 AM **Deleted:** Table 12-1 Related or possibly related AEs may result during the use of the study drug as planned (per protocol), or from abuse, withdrawal or over-dosage of the agent.

### 12.3.4 Intensity (Severity)

The intensity (synonym: severity) of clinical AEs (i.e., symptoms reported by the patient and/or signs observed by the investigator) will, in general, be assessed by the Investigator using the five-level grading system (Table 12-2; adapted from CTCAE v4.02 [17]). The system reflects the duration of the event, its impact on the subject's activities, the level of medical intervention required, and, for events assessed as related or possibly related to study drug, the action taken with study drug. The Table below is intended to provide guidance; the investigator should use judgment in assigning an intensity grade to an event. In some instances a single characteristic may determine the grade; in other instances, the overall pattern may be considered more appropriate.

For this purpose, activities of daily living (ADL) are classified into two subsets:

- *Instrumental ADL* e.g., preparing meals, shopping for groceries or clothes, using the telephone, managing money;
- Self-care ADL e.g., bathing, dressing and undressing, feeding self, using the toilet, taking medications, and not being bedridden.

Note that the Sponsor provides specific guidelines for grading injection site reactions (see Section 12.5).

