# 7.5.1 Definition of a Dose-Limiting Toxicity (DLT) Event

A DLT systemic clinical event is defined as a treatment-emergent systemic clinical event that meets **all** of the following criteria:

- is assessed by the investigator as related or possibly related to study drug (see Section 12.3.3);
- is of severity (see Section 12.3.4) Grade 2 or higher;
- is of duration >48 hours.

A DLT injection site reaction (ISR) is defined as an event that meets both of the following criteria:

- occurs at the injection site;
  - is of severity Grade 3 or higher.

A DLT *laboratory event* is defined as a confirmed, treatment-emergent laboratory finding that meets **both** of the following criteria:

- is *not* considered consistent with a concurrent clinical event that is assessed as not related or unlikely related to study drug (e.g., an accidental injury, new ART); *and*
- based on pre-specified toxicity criteria (see Section 12.5.5), represents an increase of two Grades or more compared to pre-treatment baseline value.

A subject who experiences a DLT event will not receive further doses of study drug. Unblinding may be performed to determine if a DLT event has occurred in a subject receiving DAR-901.

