#### Table 12-2. Guidelines for grading the intensity (severity) of AE

Event Characteristic				
	1 (Mild)	2 (Moderate)	3 (Marked)	4 (Extreme) [b]
Duration of symptoms	Transient, typically <48 hrs	Up to 2 weeks	>2 weeks, reversible	Symptoms / disabilities may be permanent
Impact on ADL	No limitations in ADL;	Some limitations in age-appropriate instrumental ADL	Some limitations in self-care ADL	Limitations in all activities; significant assistance required
Medication intervention	None or only OTC meds	OTC or prescription meds; provide relief	Prescription meds required; relief may be partial	Multiple meds required
Interventions other than medication	Minimal, local, or non-invasive	Minimal, local, or non-invasive	May be hospitalized <24 hr	Hospitalization >24 hr; surgery
Typical action with study drug [c]	No adjustment in study treatment regimen required	Study drug may or may not be continued	Study treatment may be discontinued	Study drug is discontinued

[a]. Grade 5 is death (fatal) and is reserved for the particular AE that is assessed as the primary cause of death. Alternative terminology in use for Grade 3 includes "Severe"; for Grade 4 includes "Life-Threatening".

[b]. Typically "Life-Threatening," that is, imminent risk of death, urgent or significant intervention required.

[c]. Applicable only if event assessed as related or possibly related to study drug.

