### 14.3 Statistical Methods

Study results will be analyzed using descriptive statistics. Adverse events will be listed per dose level and analyzed by intensity and relationship to investigational product. All other variables will be analyzed descriptively per dose level. No formal statistical comparisons are planned.

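### Table 12-2 lets the action taken with study drug enter the severity grade, but only for events judged related, so intensity is not graded independently of causality

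*Protocol*

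**What the plan says.** Section 12.3.4 of the protocol sets out how the investigator grades the intensity of clinical adverse events. The grade reflects duration, effect on activities, level of intervention and, "for events assessed as related or possibly related to study drug, the action taken with study drug". Table 12-2 carries the last element as a row on the typical action with study drug, limited by its footnote c: "Applicable only if event assessed as related or possibly related to study drug". The Grade 1 cell of that row reads "No adjustment in study treatment regimen required" and the Grade 2 cell "Study drug may or may not be continued". The Grade 3 cell allows for discontinuation, and the Grade 4 cell states it as having happened.

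On how to use the table, Section 12.3.4 says: "The Table below is intended to provide guidance; the investigator should use judgment in assigning an intensity grade to an event". It adds: "In some instances a single characteristic may determine the grade". In other instances the overall pattern may decide.

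Two other sections use the grade. Section 7.5.1 defines a systemic DLT as a related or possibly related event of Grade 2 or higher, graded under Section 12.3.4, that lasts more than 48 hours. Its consequence is: "A subject who experiences a DLT event will not receive further doses of study drug". Section 14.3 has adverse events "analyzed by intensity and relationship to investigational product".

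Relationship and action taken are also recorded for every adverse event as items of their own, in Sections 12.3.3 and 12.3.5.

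**The concern.** Safety and tolerability are the primary objective, and the adverse event tables by intensity and relationship are the main output. Those tables treat intensity and relationship as two separate descriptions of an event. They are not separate if one of the inputs to intensity is switched on by the relationship judgment. A severity distribution for related events would then partly record what was done about dosing, while the distribution for unrelated events would not, and the two could not be read side by side.

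There is also a loop. For a systemic event the grade helps to decide whether the DLT rule applies, a DLT ends dosing, and ended dosing is itself a grading characteristic. The grade is assigned by the investigator at data capture, so an analysis plan cannot readily undo this later.

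**Working it through.** No figure in the protocol is at issue, so the check is a reading of the cells against the rules.

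**1. Which events are affected.** Section 12.5.4 sends asked-about systemic and local symptoms to Table 12-4, and injection site reactions to Tables 12-4 and 12-5. Neither table has a row for action with study drug. Section 12.6 grades the listed laboratory tests on a scale of their own. What remains is clinical adverse events graded with Table 12-2. Rash and arthralgia are examples, since neither is among the expected systemic symptoms in Section 12.5.1. (The diary pages are not shown; I assume that they add neither.)

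**2. Which action cells are compatible with dosing having been stopped.**

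| Grade | Action cell in Table 12-2 | Compatible with stopping? |
|---|---|---|
| 1 | "No adjustment in study treatment regimen required" | No |
| 2 | "Study drug may or may not be continued" | Yes |
| 3 | Discontinuation possible | Yes |
| 4 | Discontinued | Yes |

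Stopping fits three of the four cells and excludes only Grade 1.

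**3. Lower boundary.** Take a mild rash of less than 48 hours with no limit on activities, no prescription medicine and only minimal measures. The investigator stops dosing, which Section 7.6.1 allows for an adverse event on judgment.

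| Input | Judged possibly related | Judged unrelated |
|---|---|---|
| Duration | Grade 1 | Grade 1 |
| Activities | Grade 1 | Grade 1 |
| Medication | Grade 1 | Grade 1 |
| Other interventions | Grade 1 | Grade 1 |
| Action with study drug | Not Grade 1; lowest fit is Grade 2 | Row does not apply |

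The clinical facts and the action are the same, but the event is graded on five inputs in one column and four in the other. Because one characteristic may determine the grade, Grade 2 is open in the first column and has no support in the second.

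**4. Moderate DLT event.** A related Grade 2 systemic event of more than 48 hours is a DLT and dosing ends. By step 2, this fits the Grade 2 action cell, so the event can stay at Grade 2 on every row.

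**5. Is the situation plausible?** The notes to Table 5-5 describe 12 subjects in the earlier phase 3 trial of SRL 172 whose immunization the investigator discontinued for reactions considered possibly or probably vaccine-related. Four of these had generalized rashes, and all reactions were considered mild or moderate. Stopping after a non-severe related event has therefore occurred with the predecessor product. The notes do not split mild from moderate or name the grading scale, so they give plausibility and not a rate.

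**6. Weight of one event.** Cohorts A1 to A3 have 10 DAR-901 recipients each, so one regraded subject moves a severity category by 1/10 = 10 percentage points. In the open-label cohorts the shift is 1/6 to 1/4 (17 to 25 points) for A4 with 4 to 6 subjects, and 1/8 to 1/5 (12.5 to 20 points) for B1 or B2 with 5 to 8.

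**The case against.** The strongest reply is that Table 12-2 is guidance. The row describes the typical action, the investigator is told to use judgment, and the overall pattern may outweigh one row. In the rash example four rows point to Grade 1, and a sensible investigator may leave it there. The Grade 1 cell also speaks of what was required, and a discretionary stop need not have been required. All this stands, and it makes misgrading a possibility and not a certainty. It does not remove the asymmetry: the text names the action taken as part of the grade and restricts it to related events.

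A reader might infer more than the protocol supports in four ways.

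- *That a moderate DLT event becomes Grade 4 because dosing stopped.* The Grade 2 cell already allows for stopping, and a note to Table 12-2 describes Grade 4 as typically life-threatening. Grade 4 is a possible misreading, not the prescribed result.
- *That the malaise rates in Table 5-5 size the problem.* Malaise is an asked-about symptom and goes to Table 12-4. Its rates were also similar on SRL 172 (13 to 23%) and placebo (11 to 18%).
- *That the loop inflates DLT counts.* An event must last more than 48 hours to be a DLT, and Table 12-2 already places that duration beyond a typical Grade 1, so the action row adds little. Regrading from Grade 2 upward cannot change DLT status.
- *That the comparison of dose levels is biased.* The same scale applies at every dose, evaluations in A1 to A3 are blinded apart from the open-label first subject, and the analysis is descriptive. A bias between doses is not shown.

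**Conclusion.** The point holds in a limited form. For clinical adverse events graded with Table 12-2, severity takes in the action taken with study drug only when the event is judged related or possibly related. Intensity and relationship are therefore not independent descriptions, although Section 14.3 analyses by both. The one place where the text favours a different grade for the same clinical picture is the step from Grade 1 to Grade 2, for a mild related event after which dosing is stopped.

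The number of such events cannot be estimated: the protocol gives no rate of mild related events with discontinuation outside the injection site and the asked-about symptoms. The conclusion assumes that Section 12.5.4 governs the asked-about symptoms, although Section 7.5.1 points to Section 12.3.4 for the severity of any systemic event. If Section 12.3.4 governed those symptoms too, the reach would be wider. This is a free improvement to the wording and does not threaten the trial's conclusions.

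**What to change.** Remove the action row and its footnote c from Table 12-2, and the matching clause from Section 12.3.4, as inputs to the grade. Grade intensity on duration, activity limitation and intervention (medication and other measures) for every event, whatever its relationship. Report relationship (Section 12.3.3) and action taken (Section 12.3.5) as variables of their own, cross-tabulated with intensity where useful.

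Leave the DLT definition and the rules for discontinuing treatment as they stand. The cost is one table row, its footnote, one clause and a line in the site training. No data are lost, because both variables are already collected. If events have already been graded, list the related or possibly related ones for which dosing was stopped and confirm that their grades rest on the clinical characteristics alone.

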#### Table 12-2. Guidelines for grading the intensity (severity) of AE

Event Characteristic				
	1 (Mild)	2 (Moderate)	3 (Marked)	4 (Extreme) [b]
Duration of symptoms	Transient, typically <48 hrs	Up to 2 weeks	>2 weeks, reversible	Symptoms / disabilities may be permanent
Impact on ADL	No limitations in ADL;	Some limitations in age-appropriate instrumental ADL	Some limitations in self-care ADL	Limitations in all activities; significant assistance required
Medication intervention	None or only OTC meds	OTC or prescription meds; provide relief	Prescription meds required; relief may be partial	Multiple meds required
Interventions other than medication	Minimal, local, or non-invasive	Minimal, local, or non-invasive	May be hospitalized <24 hr	Hospitalization >24 hr; surgery
Typical action with study drug [c]	No adjustment in study treatment regimen required	Study drug may or may not be continued	Study treatment may be discontinued	Study drug is discontinued

[a]. Grade 5 is death (fatal) and is reserved for the particular AE that is assessed as the primary cause of death. Alternative terminology in use for Grade 3 includes "Severe"; for Grade 4 includes "Life-Threatening".

[b]. Typically "Life-Threatening," that is, imminent risk of death, urgent or significant intervention required.

[c]. Applicable only if event assessed as related or possibly related to study drug.

